9.1.3 Electrocardiograms

A 12-lead ECG will be performed at approximately the same time each day. Subjects will be placed in a supine position for at least 10 minutes prior to recording an ECG. Triplicate 12-lead ECGs will be collected at the pre-dose on Day 1 (baseline) and a single ECG will be collected at other scheduled times. The screening and Day 1 ECG will be used by the PI to determine subject's eligibility for enrollment. The Day 1 ECG will be reviewed to determine if subjects are safe and appropriate to dose and will be used to determine baseline for waveform and QTc.

All ECGs will be reviewed by the PI or designee. ECGs with the following readings will be considered acceptable for study and will not be considered abnormal for study purposes unless the PI or physician designee believes they represent a new medical condition when compared to baseline ECGs. In such cases an AE will be documented and the subject will be

followed for safety evaluations as appropriate. The following pre-existing conditions identified at enrollment will not be considered adverse events:

- sinus bradycardia;
- sinus arrhythmia;
- early repolarization;
- nonspecific ST-T wave pattern or changes, mild or moderate right axis deviation;
- first degree AV block (PR interval less than 210ms is acceptable);
- nonspecific intraventricular conduction delay (QRS, or average of triplicate QRS; less than 120ms is acceptable);
- short PR interval (where no delta wave), and indeterminate axis.

The Sponsor may review all or individual screening or Day -1 ECGs or may delegate to determine if meets intention of entry criteria goal of enrolling healthy normal study subjects.

Three ECG tracings are made pre-dose. At least 2 of the 3 tracings should be acceptable/normal per (correct) machine reading and all three must be consistent with otherwise healthy normal individuals.

If a post-dose ECG demonstrates a prolonged QTc interval (>500 ms) or an increase of at least 60ms from baseline average, 2 more tracings should be captured within 10 minutes. The averaged QTc value of these 3 will be used for decision making relative to the halting rules described in [Section 9.6](#).

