9.5 Dose Escalation

The SMC will review all safety and PK data after completion of each cohort. Upon completion of review by the SMC, safety summary and PK data will be sent to the FDA for review and approval to continue with dose escalation.

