9.6 Study Halting Criteria

General:

- Any SAE
- Three or more subjects within a cohort, with the same Grade 2 event ;
- Any single Grade 3 or above finding (with the exception of aPTT as explained below);
- Evidence of hematemesis or hematochezia in 2 or more subjects
- Any other findings that, at the discretion of the PI, indicate that the study should be halted;

Electrocardiograph (ECG):

Two or more subjects within a cohort who meet any of the criteria below:

- PR: >220 ms
- QRS: >120 ms
- QTcF > 450 ms for men and >470 ms for women; or
- Change from baseline (average of pre-dose triplicate ECGs): QTcF >60 ms.

Decisions are to be based on an average QTcF value of triplicate ECGs. If an ECG demonstrates a prolonged QT interval, 2 more ECGs should be obtained over a 10 minute period. The averaged QTcF values of the 3 ECGs will then be used for decision making.

Laboratory criteria:

- Two or more subjects within a cohort have a Grade 3 increase in aPTT (confirmed on repeat) as defined by the FDA toxicity grading scale as modified for this study and as appropriate for the administration of UV-4B ([Appendix II](#)).

If any of the above events occur, the study will be halted and the SMC will review the available safety data to determine if the study should proceed as planned. If none of the events described above have been observed, dose escalation will proceed according to the protocol requirements.

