
(a) Abbreviated physical examination (general appearance, heart, lungs, skin and abdomen) Day -1, Day 8 and Day 10, and brief neurological examination (mental status, motor system, and sensory system) will be done Day -1 through Day 8 and Day 10. In addition, brief physical examinations focused on the examination of skin and oropharyngeal mucosa for evidence of bleeding and/or bruising (oral [gums] and cutaneous) will be performed Days -1 through 8, and Day 10 (including a Day 1 examination prior to the first dose and 30 minutes after the 1st dose). Symptom directed/targeted physical examinations will be done at other study time points based on subject symptoms.
 
(b) Vital signs (blood pressure and pulse rate including oral temperature and respiratory rate) taken after 10 minutes supine rest; should be taken after ECG recordings (1 hour window for pre-dose procedures).
 
(c) At pre-dose, and hourly up until 2 hours after the third dose of the investigational product per day.
 
(d) Blood pressure and pulse rate taken after 2 minutes in standing position. At pre-dose, and hourly up until 2 hours after the third dose of the investigational product per day.
 
(e) Females only.
 
(f) Postmenopausal females only.
 
(g) A subset of hematology (PLT count), serum chemistry (AST, ALT), and coagulation (INR, PT, aPTT) assessments will be collected prior to the first dose only.
 
(h) Fecal occult assessments will be performed on Day 1 starting approximately 6 hours post first dose on every stool sample. On Day 15, fecal occult assessment may be performed as per discretion of the PI, and, if positive, followed until resolution.
 
(i) Triplicate 12-lead ECGs at baseline (Day 1 pre-dose); single 12-lead ECGs obtained at the same time each day for all residential days. [ECGs will be repeated for confirmation of any stopping criteria and at the PI's discretion].
 
(j) Telemetry for at least 4 hours on Day -1 and starting at -0.5 hours prior to the first dose (Day 1) and continuously through 4 hours post the first dose. Starting at 0.5 hours prior to the 3rd dose on Day 7 continuously through 4 hours post dose. (PI discretion based on ECG results)
 
(k) Pre-dose on Day 1
 
(l) Blood samples for PK analysis will be collected at pre-dose (0 hour) and after the first dose at 0.25 (±5 min), 0.5 (±5 min), 1 (±10 min), 1.5 (±10 min), 2 (±10 min), 2.5 (±15 min), 3 (±15 min), 5 (±30 min), 6 (±30 min), 8 (±30 min) hours (8 hour sample to be collected immediately before the second dose),
 
(m) One trough sample daily within fifteen (15) minutes before the first dose
 
(n) Immediately (within fifteen minutes) before the final dose, and at 0.25 (±5 min), 0.5 (±5 min), 1 (±10 min), 1.5 (±10 min), 2 (±10 min), 2.5 (±15 min), 3 (±15 min), 5 (±30min), 6 (±30 min), 8 (±30 min), 10 (±30 min), 12 (±30 min), and 14 (±30 min) hours after the final dose;
 
(o) One sample.
 
(p) Vomitus occult assessment will be done on all vomitus
												

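### Section 9.1.3 calls for the deciding QTcF triplicate at a level above the Section 9.6 halting limits, so the protocol's texts disagree for readings between the limit and 500 ms

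*Protocol*

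**What the plan says.** Protocol Section 9.1.3 takes triplicate ECGs before dosing on Day 1; after that, "a single ECG will be collected at other scheduled times". It then sets the trigger for more: "If a post-dose ECG demonstrates a prolonged QTc interval (>500 ms) or an increase of at least 60ms from baseline average, 2 more tracings" are to be captured within 10 minutes. It ties the result to halting: "The averaged QTc value of these 3 will be used for decision making relative to the halting rules" of Section 9.6.

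Section 9.6 halts the study when two or more subjects in a cohort meet any ECG criterion. For QTcF these are "QTcF > 450 ms for men and >470 ms for women", or a change from the baseline average above 60 ms. On the deciding value it says "Decisions are to be based on an average QTcF value of triplicate ECGs", and on obtaining it, "If an ECG demonstrates a prolonged QT interval, 2 more ECGs should be obtained over a 10 minute period". No figure defines prolonged in that sentence.

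Appendix IV footnote (i) adds that "ECGs will be repeated for confirmation of any stopping criteria". It gives no number of tracings, no time window and no deciding value.

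SAP Section 10.7.6 tabulates QTcF against the same 450 and 470 ms limits, so the limits themselves are consistent across the documents. Only the trigger for the triplicate differs.

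**The concern.** The halting decision rests on an average of three tracings, and the section describing how that average is obtained does not call for it until well above the absolute limits. Under Section 9.1.3 alone, a man at 465 ms with a rise of 45 ms has passed a halting limit on a single tracing, and nothing prompts the two tracings needed to decide whether it counts. Under 9.6 or the footnote, the tracings would be taken.

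Routine committee review comes late for this purpose: "The SMC will review all safety and PK data after completion of each cohort" (Section 9.5). Within a cohort, the 9.6 limits are the ECG-specific stop, and SAP Section 6 says that meeting a halting criterion stops dosing for all subjects under treatment. The grade-based halting bullets are unlikely to substitute, because Appendix II has no QTc row and Section 9.7 has no ECG limit. With recruitment at up to two sites, the same reading could count towards a halt at one and not at the other.

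**Working it through.** **Inputs.** From Protocol 9.1.3: absolute trigger >500 ms, rise trigger at least 60 ms. From 9.6: limits >450 ms (men), >470 ms (women), change >60 ms, two or more subjects per cohort. From Section 4: cohorts of 8, 6 on active drug. Exclusion criterion 8 sets no numeric QTcF entry limit. The documents give no QTcF mean or SD and no stated figure to reproduce.

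**Step 1: compare the thresholds.** Absolute: 500 - 450 = 50 ms for men; 500 - 470 = 30 ms for women. Rise: at least 60 ms against more than 60 ms, so every reading beyond the 9.6 change limit also meets the 9.1.3 trigger and there is no gap.

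**Step 2: find the uncovered range.** With baseline B and sex-specific limit L, a reading Q exceeds 9.6 without meeting 9.1.3 when Q > L, Q ≤ 500 and Q - B < 60. In whole milliseconds this runs from L + 1 to the smaller of B + 59 and 500. It needs B + 60 > L, that is, B above about 390 ms for men and 410 ms for women. The baselines below are illustrative.

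| Baseline (ms) | Men | Women |
|---|---|---|
| 390 | none | none |
| 400 | 451-459 | none |
| 410 | 451-469 | none |
| 420 | 451-479 | 471-479 |
| 430 | 451-489 | 471-489 |
| 440 | 451-499 | 471-499 |
| 450 | 451-500 | 471-500 |

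If the 9.6 limits were the trigger, the range would be empty at every baseline.

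**Step 3: see whether 9.6 resolves it.** Its own instruction depends on a prolonged interval with no figure. Read in place, directly under the 450 and 470 ms limits, it may mean those limits. Read with 9.1.3, the only figure the protocol attaches to a prolonged QTc when calling for extra tracings is >500 ms. Both readings are available, and the protocol does not choose.

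**Step 4: one ECG (assumed values).** Take a man with baseline 410 ms (mean of three), true post-dose value 455 ms, and within-subject SD 5 or 10 ms.
- 9.1.3 trigger: P(Z > (60 - 45)/(SD × √(4/3))) = 0.005 at SD 5 and 0.097 at SD 10. The >500 ms arm adds almost nothing.
- 9.6 limit as trigger: P(Z > (450 - 455)/SD) = 0.841 at SD 5 and 0.691 at SD 10.

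**Step 5: a cohort (simulation, assumed values).** There were 60,000 cohorts of 8 with 6 active, half women, six ECGs each, and baseline triplicate means within the sex limit. The low case had means of 395 ms (men) and 410 ms (women), between-subject SD 15 and within-subject SD 6. The high case had 405, 420, 20 and 10. The between-session share of variance was 0 or 0.5. A halt needed two subjects above a limit on the mean of three, and a reading that triggered no triplicate counted as no halt.

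| True effect | 9.1.3 trigger alone | 9.6 limits as trigger |
|---|---|---|
| +40 ms, sustained | 0.03-39% | 30-94% |
| +30 ms, sustained | under 0.01% to 2.6% | 4-67% |
| None | about 0% | under 0.01% to 1.1% |

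These figures describe a site that follows 9.1.3 literally and nothing else. They show direction only.

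**The case against.** The strongest reply is that a site can comply with all three texts at once. Section 9.1.3 says when extra tracings should be taken; it does not say only then. Section 9.6 has its own instruction for two more ECGs, most naturally read against the limits just above it, and the footnote asks for repeats to confirm any stopping criterion. This stands in large part. A reader might infer that the protocol leaves readings between 450 and 500 ms unconfirmed, or that the halting limit cannot operate there. The documents do not support that. What remains is that 9.1.3 expressly claims to supply the average for the 9.6 decision and attaches a different number to it.

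The rise trigger also narrows the gap. It fires first for men with a baseline of 390 ms or below and women at 410 ms or below, and at a male baseline of 400 ms only 451-459 ms is uncovered. That is correct.

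There are backstops too. The investigator or designee reviews every ECG, 9.6 has a discretion bullet, and the Protocol Summary and Section 9.8.2 allow the SMC to be consulted during the study. These reduce the consequence, but none is a defined limit.

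A reader might take the simulated halt rates as the effect of the plan as written. They are not: their means, SDs and effect sizes are assumed, and no text says that an untriggered single reading above a limit cannot halt the study.

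Finally, a reader might see an error in the averaging rule naming QTcF but not PR or QRS. The footnote, and the 30-minute repeats for conduction change in 9.1.3, already call for further tracings there. Extending the average to those intervals is an optional harmonisation.

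**Conclusion.** The inconsistency is real and confined to QTcF. The absolute trigger in 9.1.3 lies 50 ms (men) and 30 ms (women) above the halting limits it is said to serve, while the rise trigger agrees with 9.6. The affected readings depend on baseline: none up to about 390 ms for men and 410 ms for women, widening to 451-500 and 471-500 ms at a baseline of 450 ms. These ranges follow from the protocol's own numbers. How often readings would fall in them cannot be derived, because the documents give no QTcF distribution.

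The practical consequence is that two sites, or two physicians, could handle the same reading differently under a rule that stops dosing. It is worth correcting because safety is the primary objective and the remedy is small. It does not show that the study lacks ECG protection.

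**What to change.** In Protocol Section 9.1.3, replace the trigger sentence with: *If a post-dose ECG exceeds a QTcF limit in Section 9.6 (>450 ms men, >470 ms women, or a rise >60 ms from baseline), two more tracings are taken within 10 minutes and the average of the three is used for the Section 9.6 decision.* Have Section 9.6 and Appendix IV footnote (i) refer to this rule instead of restating it. Keep >500 ms for the emergency-transfer sentence. The telemetry paragraph in 9.1.3 also starts on QTc prolongation without a figure, and ends once the average is back within 60 ms of baseline; the amendment should say which threshold starts it. The sponsor may apply the same three-tracing average to PR and QRS for uniformity.

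The cost is a short amendment and two extra tracings when a QTcF limit is passed. Under the assumed values above, that is about 0.06-4% of drug-free subjects over six ECGs. Chance QTcF halts would occur in up to 1.1% of drug-free cohorts (1.8% if all male), a rate that the existing 9.6 limits already imply when applied as written.

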Description of Study Design:	
This is a multiple-ascending dose (MAD) study with up to five cohorts of healthy subjects planned. Each cohort will consist of 8 subjects (6 active; 2 placebo). Within each cohort, subjects will be randomized to receive UV-4B oral solution or placebo solution TID (every 8 hours ± 0.5) for 7 days.
 
A Safety Monitoring Committee (SMC) review of all safety and tolerability data will be conducted after completion of each cohort. The SMC will also be consulted for any specific safety signals at any point during the study, to include dose-related trends within the normal range.
 
The SMC will review all safety and PK data after completion of each cohort. Upon completion of review by the SMC, safety summary and PK data will be sent to the Food

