9.7 Individual Dose Limiting Toxicity

- Any single grade 3 AE or Lab abnormality
- Fecal occult blood remains positive for 3 consecutive stool samples, hemorrhoids are excluded
- Evidence of frank hematemesis or hematochezia/melena of any duration
- Any clinical signs or symptoms the PI has determined is unsafe to administer IP

If an individual subject in a cohort reaches dose limit toxicity as determined by any of the above criteria, the subject will not receive any additional doses, and will be withdrawn from the study. All subjects withdrawn from the study will undergo routine follow up safety monitoring.

9.8 Safety Oversight (Safety Review Committee, Independent Safety Monitor plus Safety Monitoring Committee)

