Alkaline phosphate – increase by factor	2.0 – 2.9 x ULN	3.0 – 5.0 x ULN	>5.0 – 10.0 x ULN	>10.0 x ULN
Liver function tests – ALT, AST increase by factor	1.1 – 2.5 x ULN	2.6 – 5.0 x ULN	5.1 – 10 x ULN	>10 x ULN
Bilirubin – when accompanied by any increase in liver function test increase by factor	1.1 – 1.25 x ULN	1.26 – 1.5 x ULN	1.51 – 1.75 x ULN	>1.75 x ULN

Serum	Mild (Grade 1)	Moderate (Grade 2)	Severe (Grade 3)	Potentially Life Threatening (Grade 4)
Bilirubin – when liver function test is normal; increase by factor	1.1 – 1.5 x ULN	1.6 – 2.0 x ULN	2.1 – 3.0 x ULN	>3.0 x ULN
Cholesterol increase mg/dL	201 – 210	211 – 225	>226	--
Pancreatic enzymes – amylase, and lipase – increase by factor	1.5 – 2.0 x ULN	2.1 – 3.0 x ULN	3.1 – 5.0 x ULN	>5.0 x ULN
AE = adverse event; ALT = alanine aminotransferase; AST = aspartate aminotransferase; CRF = case report form; ECG = electrocardiogram; ULN = upper limit of normal Criteria are modified for this study based on reference values. All graded values representing a change from baseline must be reported as AEs. For clinical or laboratory observations not addressed by the toxicity grading criteria, Grade 0 = absent will be used in the AE CRF to indicate the toxicity grading criteria do not apply.				

Hematology	Mild (Grade 1)	Moderate (Grade 2)	Severe (Grade 3)	Potentially Life Threatening (Grade 4)
Hemoglobin (Female) decrease - gm/dL	10.5-11.5	9.5-10.4	8.0 – 9.4	< 8.0
Hemoglobin (Female) change from baseline value - gm/dL	Any decrease – 1.5	1.6 – 2.0	2.1 – 5.0	> 5.0
Hemoglobin (Male) decrease - gm/dL	12.5 – 13.5	10.5 – 12.4	8.5 – 10.4	< 8.5
Hemoglobin (Male) change from baseline value – gm/dL	Any decrease – 1.5	1.6 – 2.0	2.1 – 5.0	> 5.0
WBC increase - cell/mm ³	10,901 – 15,000	15,001 – 20,000	20,001 – 25,000	> 25,000
WBC decrease - cell/mm ³	2,500 – 3,500	1,500 – 2,499	1,000 – 1,499	< 1,000
Lymphocytes decrease - cell/mm ³	750 – 1,000	500 – 749	250 – 499	< 250
Neutrophils decrease – cell/mm ³	1500-2000	1000-1,499	500-999	< 500
Eosinophils increase - cell/mm ³	650 – 1500	1501 – 5000	> 5000	Hypereosinophilic
PLT decrease - /mm ³	75,000 – 99,000	50,000 – 74,999	20,000 – 49,999	<20,000
PT – increase by factor	1.0 – 1.10 x ULN	1.11 – 1.20 x ULN	1.21 – 1.25 x ULN	> 1.25 ULN
PTT – increase by factor (partial thromboplastin time)	1.0 – 1.2 x ULN	1.21 – 1.4 x ULN	1.41 – 1.5 x ULN	> 1.5 x ULN
Fibrinogen increase - mg/dL	400-500	501-600	>600	--

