2.3.1 Potential Risks (Second paragraph of Item 3 under paragraph 2) (p. 35)	
The changes in PLT count and aPTT are unlikely to be of concern in healthy subjects. The lymphoid depletion is unlikely to be of clinical concern over a short dosing period; however, the possibility that it is a manifestation of cytokine production, for example stimulation of Interleukin 4, needs to be considered. In this MAD study, careful monitoring of PLT count and coagulation parameters (aPTT, prothrombin time [PT]) as well as lymphocytes has been implemented. In addition, brief physical examinations focused on the examination of skin and oropharyngeal mucosa for evidence of bleeding and/or bruising (oral [gums] and cutaneous), as well as queries for gingival bleeding during dental care, will be performed daily.
	
The changes in PLT count and aPTT are unlikely to be of concern in healthy subjects. The lymphoid depletion is unlikely to be of clinical concern over a short dosing period; however, the possibility that it is a manifestation of cytokine production, for example stimulation of Interleukin 4, needs to be considered. In this MAD study, careful monitoring of PLT count and coagulation parameters (aPTT, prothrombin time [PT] and international normalized ratio [INR]) as well as lymphocytes has been implemented. In addition, brief physical examinations focused on the examination of skin and oropharyngeal mucosa for evidence of bleeding and/or bruising (oral [gums] and cutaneous), as well as queries for gingival bleeding during dental care, will be performed daily.
	Text correction to specify that INR is also being monitored in this study as part of the coagulation panel
4. Study Design (last sentence of paragraph 1) (p. 39)	
The study product and placebo will be masked so that the subjects and the site personnel including the PI will be blinded to the treatment assignment.
	
The study product and placebo will be masked so that the subjects and the site personnel including the PI will be blinded to the treatment assignment. Recruitment will occur at up to two investigational sites
	Clarification that recruitment will occur at up to two sites
5 Study Enrollment	Only subjects who meet all of the inclusion and none of	Only subjects who meet all of the inclusion and none of	To add that screen

Location ^a	Old Text	New Text	Rationale

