If any of the halting criteria (Protocol Section 9.6) are met, the study dosing will be halted for all subjects under treatment, although safety evaluation will continue. The SMC will review the data to determine if the study should proceed, and if any subjects need to be replaced at the same dose level.

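### Protocol section 9.6 does not settle whether one subject with a Grade 4 aPTT (above 1.5 x ULN) halts dosing in the current cohort

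*Protocol*

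**What the plan says.** The General list in protocol section 9.6 includes "Any single Grade 3 or above finding (with the exception of aPTT as explained below". The one laboratory criterion lower in the same section is "Two or more subjects within a cohort have a Grade 3 increase in aPTT (confirmed on repeat", with grading by Appendix II. The General list also halts for the same Grade 2 event in three or more subjects of a cohort, for any SAE, and at the PI's discretion. None of these carries an aPTT exception.

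Appendix II grades the test in a row labelled PTT. I take this as aPTT because 9.6 sends aPTT grading there. Grade 4 is a category of its own, in a column headed "Potentially Life Threatening (Grade 4".

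SAP section 6 states what a halt does: "the study dosing will be halted for all subjects under treatment". Protocol section 9.7 is the rule for an individual with a Grade 3 abnormality: "the subject will not receive any additional doses, and will be withdrawn from the study". It says nothing about the rest of the cohort.

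**The concern.** A halting rule has to be applied on the day a result arrives. Here the same result, one aPTT above 1.5 x ULN, leads to opposite actions depending on how far the exception reaches. If it does not halt the study, 9.7 stops the affected subject and the others continue TID unless someone chooses to intervene.

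The plainer reading also sits oddly with its neighbours. PT has no exception, so one subject in the PT Grade 3 band ("1.21 – 1.25 x ULN") halts the study. Three subjects with a Grade 2 aPTT, which starts at 1.21 x ULN, also halt it. One subject above 1.5 x ULN might not.

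The Amendment 2 table in Appendix VI carries the sponsor's general view from section 2.3.1: "The changes in PLT count and aPTT are unlikely to be of concern in healthy subjects". That can support tolerating one Grade 3 value. It does not speak to Grade 4.

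**Working it through.** The plan states no figure to reproduce. The check sets the 9.6 rules against the Appendix II bands and then bounds the exposure at stake.

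**Bands (Appendix II, Hematology, multiples of ULN)**

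| Test | Grade 1 | Grade 2 | Grade 3 | Grade 4 |
|---|---|---|---|---|
| aPTT (row PTT) | 1.0–1.2 | 1.21–1.4 | 1.41–1.5 | >1.5 |
| PT | 1.0–1.10 | 1.11–1.20 | 1.21–1.25 | >1.25 |

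**Readings of 9.6**

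- A: the exception covers aPTT at every grade, and Grade 3 in the laboratory criterion is a threshold (Grade 3 or higher).
- B: the exception covers aPTT at every grade, and Grade 3 means Grade 3 only.
- C: the exception reaches only what is explained below it, namely Grade 3, so Grade 4 stays under the General rule.

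**Automatic halt from the General and laboratory lines** (two-subject cases confirmed on repeat)

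| Result in one cohort | A | B | C |
|---|---|---|---|
| One Grade 3 | no | no | no |
| Two Grade 3 | yes | yes | yes |
| Three Grade 2 | yes | yes | yes |
| **One Grade 4, nothing else** | **no** | **no** | **yes, without a repeat** |
| One Grade 4 and one Grade 3 | yes | no | yes |
| Two Grade 4 | yes | no | yes |

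Reading B is hard to sustain. Section 9.7 also says grade 3 without adding that higher grades count, and there it must be a threshold, or a Grade 4 subject would keep dosing. Read consistently, the choice is between A and C, and they differ on an automatic halt only when there is a single Grade 4.

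**Other routes for that case**

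- SAE: 9.2.2 requires an outcome such as an immediate threat to life, or an important medical event, in the view of the PI or sponsor. A Grade 4 laboratory label is not an SAE by itself.
- PI discretion (9.6) and SMC consultation (Protocol Summary: "The SMC will also be consulted for any specific safety signals at any point during the study") depend on someone acting.
- SMC and FDA review (9.5) comes after the cohort is complete.

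**Upper bound on continued dosing**

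- Total doses: 7 days x 3 = 21 (section 4).
- Full coagulation runs daily from Day 2 (8.2.1), in the morning after dosing (7.3.2).
- Doses given by the Day d draw = 3(d − 1) + 1. Doses left = 21 − [3(d − 1) + 1] = 20 − 3(d − 1).
- Day 2: 20 − 3 = 17. Day 7: 20 − 18 = 2.

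This assumes the cohort is dosed in parallel, which the documents do not state. It counts from the draw, so doses given while the result and any repeat are awaited reduce it. It is a ceiling on doses left, not a count of doses a clearer rule would save.

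**The case against.** The strongest reply is that the exception is tied to what is explained below it, and only Grade 3 is explained. On that view one Grade 4 already halts the study, unconfirmed, and nothing is missing. This is a fair reading, and it is why the point is ambiguity. A reader might infer that 9.6 plainly allows the cohort to continue after a Grade 4 aPTT; the text does not go that far. A reader might also infer that even two Grade 4 subjects would not halt. That needs reading B, which does not fit the way 9.7 uses the same words.

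Other safeguards also count. A cohort-wide aPTT effect would meet the three-subject Grade 2 rule well below Grade 4. Coagulation is tested daily on Days 2 to 8, with same-day reports (9.1.6). Section 9.7 stops a subject at 1.41 x ULN, so reaching Grade 4 while still dosing means passing over the Grade 3 band between draws. That protection is real but thin: the band is 1.50 − 1.41 = 0.09 x ULN wide, and the readable text gives no day-to-day variability for aPTT.

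Sections that might justify the aPTT exception (2.1.3, 2.1.5, 2.2 and 2.3.1) are redacted, so a reason may exist. Amendment 1 revised 9.6 to match FDA recommendations, and the exception remains. This supports keeping the tolerance of one Grade 3. It does not tell the site what to do with one Grade 4.

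**Conclusion.** The point stands as an ambiguity in a halting rule, confined to an isolated Grade 4 aPTT in a cohort that meets neither the two-subject Grade 3 rule nor the three-subject Grade 2 rule. In that case the plainer reading gives no automatic halt and the narrower reading halts at once. The exposure is continued dosing of the rest of the current cohort: at most 17 of 21 doses per subject after a Day 2 draw, falling to 2 after a Day 7 draw, under parallel dosing.

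The readable documents give no rate of Grade 4 aPTT, so I attach no probability. The closing sentence of 9.6 might suggest that escalation would follow unchecked. It would not: 9.5 requires SMC review and FDA approval before every escalation. No endpoint or analysis is affected. The wording still merits correction, because the rule's effect should be settled before such a value occurs.

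**What to change.** Leave the General list and 9.7 as they are. Replace the laboratory criterion in 9.6 with:

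*One subject with a Grade 4 increase in aPTT, or two or more subjects within a cohort with a Grade 3 or above increase in aPTT (each confirmed on repeat).*

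Add two statements:

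- One Grade 3 aPTT is still tolerated at study level. A Grade 4 whose repeat is Grade 3 counts toward the two-subject rule only.
- Dosing of the whole cohort is held while a Grade 4 repeat is pending. Without this hold, requiring a repeat would be less protective than the narrower reading, under which one unconfirmed Grade 4 already halts.

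If the sponsor means one Grade 4 not to halt the study, 9.6 should say so and give the reason.

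The cost is an SMC review if a Grade 4 is confirmed, and a possible short hold while it is checked. A 24-hour hold would cost 24 / 8 = 3 doses, inside the limit of four missed doses in 7.3.2; the amendment should say whether held doses count toward that limit. No new visit or type of test is needed.
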